A second appointment will be scheduled to conduct the oral health examination, including intraoral scanning and 2 bitewing radiographs (BW). The responsible researcher will request the participants to provide any recently available BW, in case these are not older than 6 months. No study-related examination will be conducted before the signed parental consent form has been obtained by the responsible researcher. The participants will not be offered any treatment other than routine professional tooth cleaning, which is important for a thorough visual examination and scanning of the teeth. In case any oral disease is detected, the participants will be referred to their dentist for treatment.

If no radiographs are available from the past six months, BW of the upper and lower posterior teeth on both sides will be taken. Since radiographs are part of the participants' annual dental check-up, these will be made available to the participants' dentist. Additionally, an oral examination will be conducted, and the condition of teeth, gums and fillings will be registered. The approximal plaque accumulation will be registered by employing the approximal plaque index (21). Thereafter, the teeth will be professionally cleaned, and the presence of caries lesions will be registered based on the visual and radiographic assessments. Caries lesions will be characterized as active or inactive and classified according to the ICDAS criteria into 7 stages (22). Furthermore, the presence of other visible defects on the oral hard tissues (*i.e.* erosive – abrasive lesions) will be registered using appropriate criteria (*i.e.* BEWE index for erosive tooth wear) (2, 23).

Subsequently, both the upper and lower jaw of the participant will be scanned using the intraoral scanner (Trios 4, 3Shape Trios A/S, Denmark). Scans will be obtained using visible white and blue light (wavelength 415 nm).

At the end of the session, the participants will be classified into different risk groups (low, moderate, high) according to the clinical findings and the information collected from the diet

history and the oral hygiene habits questionnaire (Appendix 1, 2). According to this classification, the responsible researcher will set the follow-up intervals for each participant (3-12 months). All patients will be monitored for 1 year.

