The same clinical procedures will be followed on the follow-up examinations (3 or 6 months) as well as on the final examination (1-year follow-up). The diet history, the oral hygiene habits questionnaire and the BW radiographs will be repeated only on the final examination (Table. 1).

4. Statistics

Paired T-test will be conducted to identify differences between the clinical scores at the baseline and the subsequent follow-ups for the different conditions investigated (*i.e.* caries score, erosion score) (24).

Exploratory analysis of the data extracted from the 3D scans will be conducted and compared to the clinical scores. Pearson correlation coefficients between the clinical scores and scores obtained from the 3D scans will be calculated. Paired t-test will be conducted to compare the number of lesions per patient (*i.e.* caries, tooth wear) that will be detected with the 2 different methods (scanning and clinical-radiographic examination).

All statistical analysis will be conducted using a 95% level of confidence.

Information regarding the sample size calculation using power analysis is provided on the following paragraph (§5. Research subjects - Sample size calculation)

5. Research subjects

The participants in this research project will be adolescents (12-16 years old) and young adults (18-19 years old) in Denmark and in Greece respectively.

As previously mentioned, this project will assess the ability of the intraoral scanner combining fluorescence to detect and monitor initial changes in the dental hard tissues, with special focus on caries: the most prevalent oral disease. The most important benefit expected by using the fluorescence method is the detection of initial lesions on dental surfaces directly exposed to the mouth. Fissure lesions in permanent posterior teeth usually appear in the long-lasting period of tooth eruption, *i.e.* from when the tooth first appears in the mouth until it contacts with the opposite dentition (28). Eruption of the first permanent molar starts around the ages of 6-8 years, the second molar at 12-14 years (28) and the third molar at 17-18 years. During the eruption period, the posterior teeth are at a higher risk for developing fissure caries. For the second permanent molars, this period can last up to 27 months form the first appearance in the mouth (~12 years old) (29) though for the third molars this period is usually longer.

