The initial state of the caries lesion is short-lived before progression of the disease. In older patients, caries lesions in fissures are either found at more advanced stages or they have already been treated by the dentist (*i.e.* sealed, filled or extracted as in the case of third molars) (28). Although initial caries lesions can be found in older patients, such initial lesions are located on the surfaces between the teeth, which are not visible to the intraoral scanner and therefore cannot be detected using this method.

For these reasons, the age group is set from 12 to 19 years. It is necessary to conduct the study on this group of young people, as the study is expected to benefit them directly. The same benefits are not expected if the study is conducted in older adults.

The early diagnosis of initial lesions in the young participants is more beneficial as it will allow the implementation of preventive measures to stop the progression of the disease. This will decrease the complexity of the treatments needed in the target group, as the initial lesions can be treated with minimal or non-invasive approaches. Thus, the economic burden for the state regarding treatment expenses of the adolescents and the individual costs related to future dental treatment will be reduced.

Inclusion criteria:

- Young people (12-19 years old) without chronic diseases.

Exclusion criteria:

- Participants in need of complex dental treatment (*e.g.* extensive restorative work, extractions, prosthetic treatment).
- Participants using partial/complete removable dentures or other appliances (*i.e.* orthodontic devices).

Sample size calculation

Caries data was used in order to calculate the desirable sample size for the current study, as that is the most prevalent oral disease in young patients and is widely investigated in epidemiological studies (1). Therefore, data regarding initial caries lesions was used for the sample size calculation, assuming that the new method will aid dentists to detect significantly more initial caries lesions compared to traditional methods.

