For the sample size calculation, data collected by the Central Odontology Register of the Danish National Board of Health (Sundhedsstyrelsens Centrale Odontologiske Register SCOR) during the year 2017 from municipal dental clinics at 98 different municipalities in Denmark was used. According to the data, an average of 3.08 initial lesions, with a standard deviation of 1.23 were identified on 15-year old patients at the different municipalities. In this study, the desirable power was set on 90%, the level of significance on 5% and the effect size on 30% (1 lesion). By applying these parameters, the sample size was calculated to be 64 adolescents. Nevertheless, as a 10% drop-out is expected for this type of study, the final number of participants to be included in the study should be 70.

6. Risks, side effects and shortcomings in short and long term

Risks

This study will be conducted on healthy persons, on whom the procedures followed in this study are assumed to have a negligible risk.

No risk is related to the clinical visual examination.

Regarding the 3D intraoral scanning procedure, if the scan quality is poor and thus the scan is not useful for the research objectives, the scanning procedure should be repeated. This is of no risk for the patient but represents the inconvenience of a delay of the dental visit.

For the scanning using blue light (wavelength 415nm) possible risks exist. For the participant, light irritation of the mucosa and lips may result from a local, acute overexposure to the strong blue light. This irritation, though, is mild and temporary. For the operator, possible harm to the eyes, especially on the lenses and the retinal tissues, may be caused by long-term cumulative exposure to blue light. These risks are not particular for this specific intraoral device but are

common to any dental equipment that uses blue light. Having these risks in mind, the equipment will be used properly and with care: the exposure time will be limited to 15 seconds per tooth and direct exposure to mucous membranes will be avoided. The equipment will be started only after it has been inserted into the patient's mouth. The operator will avoid looking directly into the mouth and instead will look on the computer screen during the scanning procedure. Eye-protection goggles filtering light under 500 nm are suggested to be used by the operator.

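### The sample size of 64 matches two independent groups of 32, but the planned comparison is paired within one cohort, so the stated 90% power does not belong to it

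*Combined protocol and SAP*

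**What the plan says.** Section 5 (Sample size calculation) bases the number of participants on initial caries lesions, "assuming that the new method will aid dentists to detect significantly more initial caries lesions compared to traditional methods". The inputs are 2017 register data from 98 Danish municipalities: a mean of 3.08 lesions, "with a standard deviation of 1.23 were identified on 15-year old patients at the different municipalities". Power is set at 90%, significance at 5%, and the effect at 30%, which is equated with 1 lesion. The result is "By applying these parameters, the sample size was calculated to be 64 adolescents", raised to 70 for 10% drop-out. The paragraph names no test, number of groups or sidedness, and gives no SD of differences and no correlation between methods.

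Section 4 (Statistics) states the comparison of scanning with clinical-radiographic examination: "Paired t-test will be conducted to compare the number of lesions per patient". It stands in a paragraph that opens "Exploratory analysis of the data extracted from the 3D scans will be conducted and compared to the clinical scores". The other t-test in that section, follow-up against baseline, is also paired.

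Section 3 (Clinical and radiographic examination) describes a single cohort. Each participant is examined clinically and then: "Subsequently, both the upper and lower jaw of the participant will be scanned using the intraoral scanner". Existing bitewings are accepted "in case these are not older than 6 months". That affects the timing of the radiograph but not the pairing, since both counts still come from the same participant.

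**The concern.** A sample size has to be computed for the test that will be run. Two independent groups and one group measured twice use different variances. The first uses the between-patient SD in each group. The second uses the SD of the difference within a participant, which depends on how closely the two methods agree across participants. The protocol supplies a single SD from a register of routine examinations and says nothing about differences or agreement.

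The 90% is the only power statement in the document. If it was computed for a design the study does not have, a reader cannot use it to judge whether the study is too large, adequate or too small for its main question, nor to interpret a non-significant result.

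**Working it through.** **Inputs.** From section 5: mean 3.08, SD 1.23, power 90%, significance 5%, difference 1 lesion or 30%. These two differences are not equal: 0.30 x 3.08 = 0.924 lesions, and 1/3.08 = 32.5%. Sidedness is not stated, so both were tried.

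**Step 1: reproduce 64.** For two independent groups by the normal formula, n per group = 2 x SD² x (z₁₋α/₂ + z₁₋β)² / d². With d = 1, two-sided: 2 x 1.23² x (1.960 + 1.282)² = 3.0258 x 10.507 = 31.79, so 32 per group and 64 in total. All variants with SD 1.23:

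| Two independent groups (total) | Normal | Exact t |
|---|---|---|
| 1 lesion, two-sided | **64** | 66 |
| 1 lesion, one-sided | 52 | 54 |
| 0.924 lesions, two-sided | 76 | 78 |
| 0.924 lesions, one-sided | 62 | **64** |

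Two variants give 64, and both are 2 x 32. The sidedness and the exact difference behind the figure therefore cannot be recovered from it.

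**Step 2: try paired readings.** Pairs needed for 90% power by exact t:

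| Paired reading | 1 lesion, two-sided | 1 lesion, one-sided | 0.924, two-sided | 0.924, one-sided |
|---|---|---|---|---|
| 1.23 is the SD of differences | 18 | 15 | 21 | 17 |
| 1.23 per method, correlation 0 | 34 | 28 | 40 | 32 |

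Reading 30% as a standardised paired difference of 0.3 gives 119 (two-sided) or 97 (one-sided). None of these is 64.

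**Step 3: what would make 64 pairs right?** If both methods have SD s and correlation r, the SD of differences is s x √(2(1 − r)). With 64 pairs, two-sided exact t, 90% power needs an SD of differences of 2.430 (1 lesion) or 2.245 (0.924). With s = 1.23:

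- 1 lesion: r = 1 − 2.430²/(2 x 1.23²) = −0.95
- 0.924 lesions: r = 1 − 2.245²/(2 x 1.23²) = −0.67

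A strong negative correlation between two lesion counts in the same mouths is not credible.

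**Step 4: power of the planned paired test.** Enrolment of 70 with 10% drop-out leaves 70 x 0.9 = 63 pairs; a baseline comparison would have about 70. Two-sided 5%, exact t, shown for 1 lesion / 0.924 lesions. Only the first row uses the protocol's SD. The others are assumptions, needed if 1.23 describes municipality averages; 1.755 is √3.08, the Poisson value.

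| Patient SD per method | 63 pairs, r = 0 | 63 pairs, r = 0.5 | 70 pairs, r = 0 |
|---|---|---|---|
| 1.23 | 99.4% / 98.6% | above 99.9% / above 99.9% | 99.7% / 99.2% |
| 1.755 | 88% / 83% | 99% / 98% | 91% / 87% |
| 2 | 79% / 72% | 97% / 95% | 83% / 77% |
| 3 | 45% / 40% | 74% / 67% | 49% / 44% |

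For 63 pairs and 1 lesion, 90% is reached at a correlation of at least 0.06 (SD 1.755), 0.27 (SD 2) or 0.68 (SD 3).

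**Step 5: limit on the SD of differences.** The standardised difference detectable with 90% power is 0.4149 with 63 pairs and 0.3929 with 70. Dividing each difference by these gives the largest admissible SD of differences: 2.41 / 2.23 with 63 pairs and 2.54 / 2.35 with 70.

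**The case against.** The strongest reply is that nothing has been lost. The stated inputs do give 64 by the ordinary two-sided normal formula with 1 lesion. Read plainly, 1.23 describes lesions in 15-year-old patients. If it is a patient SD that also holds for the scanner, the paired test has at least 98.6% power even for 0.924 lesions at any correlation of 0 or more. The lower figures need SDs that appear nowhere in the protocol, and the worst of them also assume no correlation between two counts in the same mouths. A baseline comparison would have about 70 pairs, which lifts the Poisson case at correlation 0 from 88% to 91% for 1 lesion. The 30% may simply be 1 lesion rounded. The comparison is introduced as exploratory.

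Much of this stands. Low power is not demonstrated, the larger SDs are assumptions, and the two-group origin of 64 is inferred by back-calculation because the protocol names no formula. But the reassurance rests on two premises that the protocol does not establish: that 1.23 is a between-patient SD, and that it applies to scanner counts. The reference to the different municipalities leaves the first open, and no scanner data are given for the second. The exploratory label does not remove the point either, because section 5 builds the sample size on this comparison. Nor is 30% versus 1 lesion negligible: in the two-sided normal two-group formula it moves the total from 64 to 76.

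**Conclusion.** The concern holds. Among the readings tried, the stated inputs give 64 only as two independent groups of 32, while the design is one cohort compared by paired t-test. The 90% is therefore not the power of the planned comparison, and that power cannot be computed from the documents because the SD of within-participant differences is missing.

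The direction of the error is open. If 1.23 is the patient SD under both methods and the correlation is not negative, the error is conservative. If 1.23 is a spread of municipality averages, power could lie above or below 90%, depending on a patient SD and correlation that would have to be assumed. The power figures take a two-sided 5% test, equal SDs for the two methods where a correlation is used, and the t-test's normal approximation for lesion counts. This should be fixed because it is the only power statement, but it is no evidence that 70 participants are too few.

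**What to change.** Restate the sample-size paragraph in section 5 for the paired test, for example:

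> The number of initial lesions per participant is compared between scanning and clinical-radiographic examination at [visit] by two-sided paired t-test at the 5% level. The difference of interest is [1 lesion, 32% of 3.08 / 0.924 lesions, 30% of 3.08]. With 70 enrolled and 10% drop-out, 63 evaluable pairs give 90% power for a mean difference of 0.415 SD of the differences, that is, for [1 lesion if that SD is at most 2.41 / 0.924 lesions if it is at most 2.23]. We assume an SD of differences of [value], from [source].

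If the comparison is made at baseline with about 70 pairs, the limits become 2.54 and 2.35. If no source exists for the SD of differences, show power over a range instead. With 63 pairs:

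| SD of differences | 1 lesion | 0.924 lesions |
|---|---|---|
| 1.5 | 99.9% | 99.8% |
| 2 | 97% | 95% |
| 2.5 | 88% | 82% |
| 3 | 74% | 67% |

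Also state whether 1.23 is a spread between patients or between municipality averages.

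The cost is one reworded paragraph, one choice of difference, and one justified input or table. Enrolment stays at 70. If the justified SD exceeds the limit, restate the detectable difference (0.4149 x 3 = 1.24 lesions with 63 pairs at an SD of 3) or the power.

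### Minor: enrolling 70 with the expected 10% drop-out leaves 63 participants, one short of the calculated 64; the sentence needs correcting but the effect on power is very small

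*Combined protocol and SAP*

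**What the plan says.** The sample-size paragraph in section 5 takes its planning values from Danish register data: "an average of 3.08 initial lesions, with a standard deviation of 1.23 were identified on 15-year old patients". With 90% power, 5% significance and a difference of 30%, equated to 1 lesion, it states that "the sample size was calculated to be 64 adolescents". It then adds the drop-out allowance: a "10% drop-out is expected for this type of study, the final number of participants to be included in the study should be 70". No formula is given for the step from 64 to 70.

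Three other places bear on the point:

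- Section 3 (Information about the project) lets participants withdraw at any time. No section provides for replacing them.
- Section 3 (Clinical and radiographic examination) puts the clinical-radiographic examination and the scan in the same appointment, starting at baseline.
- Section 4 (Statistics) gives the comparison of the two methods: "Paired t-test will be conducted to compare the number of lesions per patient". It does not say which visit this uses. The section also plans paired t-tests of clinical scores between baseline and follow-up.

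**The concern.** The only purpose of the 70 is to protect the 64 against the expected loss. If 10% of those enrolled are lost, the number left should be at least 64, and it is not. The usual cause is adding 10% of the required number instead of dividing by the retained fraction. A sample-size figure that fails under its own stated assumption should be corrected, because readers will take it that 10% loss is fully covered. At stake is the accuracy of a stated design figure and, at most, a fraction of a percentage point of power.

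**Working it through.** **Inputs (section 5):** SD 1.23; difference 1 lesion; power 90%; significance 5%; required number 64; drop-out 10%; enrolment 70. Sidedness is not stated, and two-sided is assumed.

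**1. Reproduce the 64.** For two independent groups, normal approximation:

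n per group = 2 × [SD × (z₀.₉₇₅ + z₀.₉₀) / Δ]² = 2 × [1.23 × (1.960 + 1.282) / 1]² = 31.8, rounded up to 32, so 2 × 32 = 64.

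This matches exactly. Neither variant tried does: a one-sided test gives 52, and an unrounded 30% of 3.08 (0.924 lesion), two-sided, gives 76.

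**2. Reproduce the 70.** 64 × 1.10 = 70.4, which rounds down to 70. This route is inferred, since the protocol shows none.

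**3. Apply the stated drop-out to those enrolled.**

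| Enrolled | Expected completers at 10% loss |
|---|---|
| 70 | 70 × 0.90 = 63.0 |
| 71 | 71 × 0.90 = 63.9 |
| 72 | 72 × 0.90 = 64.8 |

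The number needed is 64 / (1 − 0.10) = 71.1, i.e. 72. Rounding 70.4 up to 71 would not have been enough.

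**4. What 70 does tolerate.** 70 − 64 = 6 losses, and 6 / 70 = 8.6%.

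**5. Chance of keeping 64.** If each participant drops out independently with probability 10% (an assumption), P(at most 6 losses of 70) = 44% and P(at most 8 losses of 72) = 71%.

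**6. Cost in power,** on the calculation from step 1. Power = Φ[Δ / (SD × √(2/n)) − 1.960], with n per group.

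- 64 participants (n = 32): Φ(3.252 − 1.960) = Φ(1.292) = 90.2%.
- 63 participants (n = 31.5): Φ(3.227 − 1.960) = Φ(1.267) = 89.7%.

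The loss is just under 0.5 percentage points. With the t distribution the figures are 89.3% and 88.8%, a loss of the same size.

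**7. Under the planned paired test.** The documents give no SD for the within-person difference. Assume SD 1.23 for each method and a within-person correlation ρ between 0 and 0.7, so that SD of the difference = 1.23 × √[2(1 − ρ)], from 1.739 down to 0.953. Then 34 down to 12 participants give 90% power for a 1-lesion difference, and 63 pairs give at least 99.4%. Without assuming a correlation, 63 pairs keep 90% power for any SD of the difference up to about 2.41.

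**The case against.** The strongest reply is that nothing is lost in practice. It has four parts.

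- **The comparison that 64 was sized for need not suffer drop-out.** The calculation rests on the scanner finding more initial lesions than traditional methods. Both assessments are made at the baseline appointment, so all 70 can contribute a pair there, which exceeds 64. This stands, provided those enrolled attend baseline and have a usable scan.
- **One participant is immaterial.** The power loss is under half a point, and 10% is only a general expectation. This also stands. The 44% against 71% contrast should be read in that light: it treats 63 as failure and 64 as success, although the two hardly differ in power.
- **64 is not a true minimum for a paired test.** It reproduces as two independent groups, while section 4 plans a within-person comparison. This is fair, but the plan cannot claim the surplus as written. The surplus depends on an assumed correlation and on 1.23 being a between-patient SD, and the text describes that SD in terms of the different municipalities. The mismatch is a separate matter.
- **The gap between 70 and 72 is rounding.** This does not stand. 63 is below 64, and even 71 enrolled gives an expected 63.9.

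A reader might also infer that the 1-year analyses will miss their required number. The documents do not support that. They give no effect size, SD of change or target for the baseline-to-follow-up tests, and 64 was derived from a lesion count at one time, not from change over a year.

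**Conclusion.** The point holds as a minor correction. Under the protocol's own 10%, enrolling 70 leaves 63 expected completers against a calculated 64; the consistent figure is 72. This is simple arithmetic on stated numbers, and no provision for replacement makes up the difference. Only the explanation (multiplying by 1.10 and rounding down) is an inference.

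The size is one expected completer. The power figures, 89.7% against 90.2%, rest on the reconstructed two-sided, two-group calculation. It would be wrong to conclude from this that the study is underpowered: the baseline comparison of methods can use all 70, and under the paired assumptions shown above 63 pairs are ample for a 1-lesion difference.

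**What to change.** Keep 70 and correct the sentence in section 5. Suggested content: *70 participants will be included, which allows for up to 6 losses (8.6%) while retaining 64. With 10% drop-out, 63 completers are expected, giving about 89.7% power on the same calculation; full allowance for 10% would need 64 / 0.90, i.e. 72.*

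Enrolling 72 would also be consistent, at the cost of two more participants, but the gain in power does not call for it.

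The recommended change costs one sentence. Recruitment, visits and analysis are unaffected. The only downside is a slightly lower stated drop-out tolerance. If the base number is ever recalculated for the paired design, the allowance should again be made by dividing by the retained fraction.
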